5.1 Inclusion criteria

- age: over 18 years.
- subjects eligible for TKA.

5.2 Exclusion criteria

- QAB (quadriceps activation battery) < 6 the day before the operation [12].
- neurological or musculoskeletal diseases (different from the causes that which led the patient to the TKA), which may interfere with the quadriceps muscle activation or with motor performance of the subject.
- Uncooperative subjects.

6 Design

Prospective observational study. See *Attachment A*.

6.1 General design

The patients scheduled for TKA will be recruited through the criteria mentioned above; moreover, healthy subjects will be recruited as control group. The patients will be assessed through a motor ability test (TUG), a referred pain scale, and a quadriceps isometric contractions session recorded with surface electromyography. The assessment sessions will be conducted the day before the operation and on the first and third postoperative day. The control group will be exposed once to the same assessments, with the EMG applied on the quadriceps muscle of the dominant limb.

The sEMG data will be acquired by asking the subjects to perform the following tasks: "homolateral knee extension", "homolateral hip flexion" and "contralateral hip extension with a contemporary homolateral hip flexion". Each task will be repeated twice and the execution order will be randomized. The subject will be placed in the supine position and three bands will be positioned respectively at the level of the malleolus and the inferior margin of the patella in order to immobilise the inferior limb and ensure an isometric contraction of the quadriceps, while keeping

the biomechanical context unchanged. For each subject belonging to the two study groups, the same setting will be used. During the data acquisitions, every subject will be encouraged to perform each contraction with the maximum strength. The performance of tasks will be video recorded in order to monitor the correct execution.

The NRS scale will be administered to the patients after each quadriceps evaluation session, while the TUG test will be conducted the day before the operation and on the third day after surgery.

In the first and third day after surgery, the session will take place after 3pm in order to allow the patients to participate in both of the physiotherapeutic treatments provided by the Humanitas Clinic Institute.

The TUG test consists in asking the patient to stand up from a chair, walk at spontaneous speed, turn back at a cone placed at a distance of 3 metres and sit back down on the chair. The patient will be timed starting from the operator mark and stopping when the patient has resumed the seated position on the chair. The test will be performed once in a session, with a mock test before.

The NRS scale consists of one 10cm segment, numbered from 0 to 10 on which the subject has to quantify their pain perception where 0 equals “no pain” and 10 equals “the worse pain ever perceived”.

Every assessment session will be conducted by one expert operator.

7 Statistical considerations

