4.2 Endpoints

4.2.1 Primary endpoint

The primary aim is to observe possible activation alterations of the quadriceps femoris, more specifically of the vastus medialis, lateralis and rectus femoris muscles, by means of electromyographic signal acquisition. The subject will be asked to perform different tasks in isometric contractions, without changing the biomechanical context. The subjects will be asked to perform a homolateral knee extension, a homolateral hip flexion, a contralateral hip extension with

a contemporary homolateral hip flexion. The activation of the three muscles will be recorded through surface electromyography (sEMG) with four channels (FREEEMG 1000, BTS SpA). The electromyographic surface sensors will be positioned following the European SENIAM guidelines regarding vastus medialis, lateralis and rectus femoris of quadriceps femoris homolateral in terms of surgery access, in order to evaluate the activation intensity during the different tasks [11].

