7.1 Sample Size

The primary outcome of this study is the EMG signal detected during different isometric contractions of the quadriceps muscle. In the published scientific literature, there is insufficient data to define the minimal statistically significant difference for this outcome. Therefore, it is not possible to calculate the sample size. Some studies exist which compare the muscular activation in the inferior limb between healthy subjects and patients who have undergone PTG, with 10 subjects for each group [13]. In this study, 15 healthy subjects and 15 patients will be recruited; it is estimated that this sample will be enough to obtain a preliminary valuation of the differences between groups.

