7.2 Analysis

The statistical analysis will be carried out at the end of the data collection, using the SPSS 20.0 software. The categorical variables will be described via mean and standard deviation or median and interquartile range. The normality of the demographic variables and the outcome measures will be evaluated through the Kolmogorov-Smirnov test.

The t Student test (with normal variables) or the Mann-Whitney test (with non-normal variables) will be used to verify the pre-intervention homogeneity of the demographic variables. The mixed models ANOVA test for repeated measures will be used to analyse possible differences inter-groups and intra-groups. A post hoc analysis will be conducted in the eventuality of significant outcomes. Linear regression will be used to investigate the correlation between the EMG outcomes and the secondary outcomes (NRS and TUG).

The threshold value for the statistical significance will be fixed at 0.05.

8 Withdrawal from the study

Subjects who decide to leave the study for any reason will be immediately excluded from it. The subjects will be also informed about the possibility of withdrawal from the study at every session provided for by the protocol, including during the planned follow-up period, giving prior notification to any of the experimenters. Data acquired from those subjects who do not complete the study will be excluded from the analysis.

9 Forms and procedures for the data collection and management

The demographic and outcome data will be input into an anonymous form within an Excel sheet (*Attachment B*). This data will be collected by two experimenters in order to minimise any errors and will be saved in password-protected electronic format.

10 Ethical considerations

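### The effort-dependent EMG outcome has no fixed form of encouragement and no masked signal processing, so uneven handling could create, enlarge or reduce the patient difference

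*Combined protocol and SAP*

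**What the plan says.** Section 7.1 names the outcome: "The primary outcome of this study is the EMG signal detected during different isometric contractions of the quadriceps muscle". Section 4.2.1 adds that the sensors are placed "in order to evaluate the activation intensity during the different tasks". The contractions are voluntary, and under section 6.1 "every subject will be encouraged to perform each contraction with the maximum strength". That section does not say who gives the encouragement, in what words or for how long.

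On who is present and what they can see, section 6.1 states:

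- "Every assessment session will be conducted by one expert operator".
- For patients, "The assessment sessions will be conducted the day before the operation and on the first and third postoperative day".
- For healthy subjects, "The control group will be exposed once to the same assessments, with the EMG applied on the quadriceps muscle of the dominant limb".

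Section 3 (Rationale) already expects reduced quadriceps activation from the first day after surgery.

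The plan has four features that bear on consistency. Section 6.1 uses the same set-up in both groups and randomises the order of the tasks. It also says: "The performance of tasks will be video recorded in order to monitor the correct execution". Section 9, on data collection and management, says: "This data will be collected by two experimenters in order to minimise any errors".

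The text describes no masking of the operator, the EMG processing or the analysis. It also gives no amplitude measure, analysis window or normalisation for the EMG.

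**The concern.** EMG amplitude in a voluntary maximal contraction depends on how hard the subject tries, and that depends partly on how the subject is urged. If urging differs systematically between a healthy volunteer and a patient on day 1, or between the same patient before and after surgery, the outcome differs for a reason unrelated to AMI. Choices made later, in picking a window or judging whether a repetition was properly executed, can have the same effect if the person making them knows the group and session.

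The bedside operator can hardly be masked, because an operated knee is visible and the sessions are tied to the day of surgery. Signal files can be masked, and encouragement can be standardised. The plan does neither. At stake is whether a lower post-operative amplitude, or the absence of one, can be read as information about quadriceps activation. A larger sample would not remove such a bias.

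**Working it through.** **Do the existing safeguards cover this?**

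| Feature | What it controls | Group or session expectation? |
|---|---|---|
| Same set-up in both groups (6.1) | Position and fixation | No; it does not script the encouragement |
| Randomised task order (6.1) | Order effects within a session | No |
| Video (6.1) | Correct execution | No; no judge, rule or timing relative to the amplitude is given |
| Two experimenters (9) | Data errors | No; masking is not mentioned |

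**Size.** The plan has no figure to reproduce: section 7.1 states that no sample size calculation was possible and gives no SD or effect size. The following is an illustration.

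Inputs from the plan: 15 patients and 15 healthy subjects (7.1); significance threshold 0.05 (7.2).

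Assumptions: two-sided testing; no true difference; a systematic shift b of 10% or 5% in amplitude; an SD s of 20% or 30%. Simple t tests stand in for the planned mixed-model ANOVA.

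*Patients against healthy subjects.* df = 15 + 15 − 2 = 28, critical t = 2.048, noncentrality = (b/s)/√(1/15 + 1/15) = (b/s)/0.365.

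*Patients, before against after.* Here s is the SD of the paired differences. df = 14, critical t = 2.145, noncentrality = (b/s) × √15 = (b/s) × 3.873.

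The chance of a significant result is the probability that a noncentral t variable falls beyond ± the critical value.

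| Shift b | SD s | b/s | Noncentrality, 15 v 15 | Significant, 15 v 15 | Noncentrality, paired | Significant, paired |
|---|---|---|---|---|---|---|
| 10% | 20% | 0.50 | 1.37 | 26.2% | 1.94 | 43.8% |
| 10% | 30% | 0.33 | 0.91 | 14.3% | 1.29 | 22.5% |
| 5% | 20% | 0.25 | 0.68 | 10.1% | 0.97 | 14.7% |
| 5% | 30% | 0.17 | 0.46 | 7.3% | 0.65 | 9.2% |

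Without a shift, each entry would be 5%. With a wider SD of 50%, a 10% shift gives 8.3% for 15 v 15 (b/s = 0.20), so the result depends strongly on an SD that the plan does not supply.

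The two designs must be kept apart. Urging patients less than healthy volunteers concerns the 15 v 15 columns. The paired columns apply only if urging differs between sessions of the same patient.

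**The case against.** The strongest case against the point has five parts.

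- **Direction.** A reader might infer that the operator will go easier on a painful day 1 patient, so that any bias favours the expected deficit. The documents do not support this. An operator could equally push a reluctant patient harder. The expectation in section 3 is a reason for care, not evidence of direction.
- **Rejected repetitions.** A reader might also infer that repetitions will be dropped after the signal is seen. Nothing says so: video is kept to monitor execution, and neither dropping nor averaging of the two repetitions is described. A written rule is a precaution, not a correction of a stated practice.
- **Mitigating features.** Encouragement is nominally the same for every subject and contraction, and the set-up is common. If urging is weaker throughout a session, all three tasks are affected, so contrasts between tasks are less exposed than the overall level. This stands, but the plan also compares groups and sessions, where the level matters.
- **Silence.** That the operator gives the encouragement is inferred, and unmasked processing is inferred from a text that describes no processing at all. A fixed pipeline would by itself remove most discretion over windows. This also stands. Knowledge of the group is least certain at the pre-operative session.
- **Claims.** The protocol speaks of differences that might be associated with AMI and of a preliminary assessment, so it does not commit itself to reporting any deficit as AMI.

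What remains is that an effort-dependent outcome is collected and processed without two inexpensive protections.

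**Conclusion.** The point holds as a risk to interpretation. Uneven encouragement or unmasked signal handling could create, enlarge or reduce the patient-control or pre-post difference, and no stated safeguard prevents this. The documents fix neither size nor direction, and they do not show that bias will occur.

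Under the stated assumptions, a 10% shift raises the chance of a false significant result from 5% to about 14–26% between groups and 23–44% in paired comparisons. A 5% shift raises it to about 7–10% and 9–15%. The paired figures should not be quoted for the comparison with healthy subjects. All of them rest on assumed shifts and SDs, and on t tests in place of the planned ANOVA.

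The sponsor should act because the remedy is cheap, while accepting that this is a preliminary observational study of 30 subjects.

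**What to change.** **Section 6.1.** Give the command and encouragement in fixed wording and for a fixed duration, from a script or a recording, identical for both groups and all sessions. Judge correct execution from the video by a written rule, before the EMG amplitude of that repetition is seen.

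**Section 9.** Export the EMG files under a random code that carries neither group nor session. Process them with one fixed automatic pipeline and window, where possible by the experimenter who did not run that session. Unlock the code only after the amplitudes are saved.

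Both parts are needed, because masked processing cannot undo a bias introduced while the signal is being recorded.

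**Cost.** A script or audio file, a coding list and slightly longer data handling. The plan does not say that the second experimenter processes EMG or stays away from the sessions, so the division of work has to be settled. If both attend, masking is incomplete. The change does not separate pain-limited effort from AMI, and the report should say so.

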7.1 Sample Size

The primary outcome of this study is the EMG signal detected during different isometric contractions of the quadriceps muscle. In the published scientific literature, there is insufficient data to define the minimal statistically significant difference for this outcome. Therefore, it is not possible to calculate the sample size. Some studies exist which compare the muscular activation in the inferior limb between healthy subjects and patients who have undergone PTG, with 10 subjects for each group [13]. In this study, 15 healthy subjects and 15 patients will be recruited; it is estimated that this sample will be enough to obtain a preliminary valuation of the differences between groups.

7.2 Analysis

The statistical analysis will be carried out at the end of the data collection, using the SPSS 20.0 software. The categorical variables will be described via mean and standard deviation or median and interquartile range. The normality of the demographic variables and the outcome measures will be evaluated through the Kolmogorov-Smirnov test.

The t Student test (with normal variables) or the Mann-Whitney test (with non-normal variables) will be used to verify the pre-intervention homogeneity of the demographic variables. The mixed models ANOVA test for repeated measures will be used to analyse possible differences inter-groups and intra-groups. A post hoc analysis will be conducted in the eventuality of significant outcomes. Linear regression will be used to investigate the correlation between the EMG outcomes and the secondary outcomes (NRS and TUG).

The threshold value for the statistical significance will be fixed at 0.05.

8 Withdrawal from the study

Subjects who decide to leave the study for any reason will be immediately excluded from it. The subjects will be also informed about the possibility of withdrawal from the study at every session provided for by the protocol, including during the planned follow-up period, giving prior notification to any of the experimenters. Data acquired from those subjects who do not complete the study will be excluded from the analysis.

9 Forms and procedures for the data collection and management

The demographic and outcome data will be input into an anonymous form within an Excel sheet (*Attachment B*). This data will be collected by two experimenters in order to minimise any errors and will be saved in password-protected electronic format.

10 Ethical considerations

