4.2.2 Secondary endpoint

The secondary aim is to understand whether there is a correlation between the acquired surface EMG data and the pain referred by the patient and the patient's functional ability. The secondary outcomes will be the pain referred by the patient and the patient's functional ability. The referred pain will be assessed through the Numeric Rating Scale (NRS) at the beginning of every session. The functional ability will be assessed with the Timed Up and Go Test (TUG) on the third day post-surgery and via a descriptive analysis on the patient's deambulation autonomy, considering the following characteristics: ambulatory aids, need for supervision or assistance, and maximum distance covered.

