10.2 Subject identification – Data protection

All data related to data acquisition and analysis and all the information related to each individual subject shall be handled in the strictest confidence and to the fullest extent of the applicable law. Privacy shall thus be safeguarded, and no information shall be made public. Each subject will be identified with an ID (*Attachment B*). The name and surname of the subject will not be required. The data required will pertain to sex and age. Only those personnel actively involved in the study will have access to the database. Each subject will be informed about data protection by means of an appropriate form in this regard (*attachment D*) and will be asked to sign an informed consent form in order to participate in the study.

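### Section 7.2 describes categorical variables by mean/SD or median/IQR and gives no rule for counts and percentages; sex is also sent to tests meant for non-categorical data, with little numerical effect

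*Combined protocol and SAP*

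**What the plan says.** Section 7.2 (Analysis) contains the only descriptive rule in the document: "The categorical variables will be described via mean and standard deviation or median and interquartile range". It continues: "The normality of the demographic variables and the outcome measures will be evaluated through the Kolmogorov-Smirnov test". For the comparison of the groups on demographics at baseline, it says: "The t Student test (with normal variables) or the Mann-Whitney test (with non-normal variables) will be used to verify the pre-intervention homogeneity". Neither 7.2 nor the statistical paragraph of the synopsis mentions counts, percentages, chi-square or Fisher's exact test.

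Two other sections show which categorical variables are collected:

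- Section 10.2, on the personal data held for each subject: "The data required will pertain to sex and age".
- Section 4.2.2, where functional ability is assessed by the TUG on the third day and also "via a descriptive analysis on the patient's deambulation autonomy, considering the following characteristics: ambulatory aids, need for supervision or assistance, and maximum distance covered".

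The regression sentence in 7.2 takes only NRS and TUG forward as secondary outcomes.

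**The concern.** Mean with SD and median with IQR are summaries for numeric data. The plan applies them to categorical variables and says nothing about how numeric variables are to be described. At least three variables are affected: sex, type of walking aid, and need for supervision or assistance.

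The walking items are where this matters most. They enter no regression and 7.2 gives them no test, so the descriptive summary is all that will be reported on them. A reader will want to know how many of the 15 patients used each aid and how many needed help, and the stated rule does not produce those numbers.

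For sex there is a second, smaller problem. A normality test on a two-valued variable serves no purpose, and no test for categorical data is named. Patients and healthy subjects are not randomised and no matching is stated, so a clear comparison of sex between the groups is useful.

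**Working it through.** The plan states no derived figure on this point, so there is none to reproduce. Inputs from the documents are 15 patients and 15 healthy subjects (7.1) and a significance threshold of 0.05 (7.2), taken as two-sided because sidedness is not stated. The documents give no sex split, aid split or coding. Those below are assumptions for illustration.

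**1. Walking aid (unordered).** Take 2 patients with no aid, 8 on crutches and 5 on a walker, and change only the numeric codes:

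| Codes (none, crutches, walker) | Mean | SD | Median |
|---|---|---|---|
| 0, 1, 2 | (0 + 8 + 10)/15 = 1.2 | 0.68 | 1 |
| 1, 2, 0 | (2 + 16 + 0)/15 = 1.2 | 0.94 | 2 |
| 0, 2, 1 | (0 + 16 + 5)/15 = 1.4 | 0.74 | 2 |

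The patients are the same in every row, so the summary reflects the coding.

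**2. Supervision or assistance.** Suppose need for help is coded 0/1. With 15 values, the median is the 8th in order. The lower quartile is the 4th value, or halfway between the 4th and 5th, depending on the definition. The upper quartile is the 12th value, or halfway between the 11th and 12th.

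- With 8, 9 or 10 patients needing help there are 7, 6 or 5 zeros.
- In all three cases the 4th and 5th values are 0 and the 8th, 11th and 12th are 1.
- The report is median 1 (IQR 0 to 1) each time, so the count cannot be recovered.

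Under the mean and SD option, the mean of a 0/1 code is the proportion. The count could then be worked back, but it would not be reported.

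**3. Sex: summary.** For 10 of 15 coded 0/1, the mean is 10/15 = 0.67, the SD 0.49, and the median 1 (IQR 0 to 1). The mean is the proportion; the SD and IQR add nothing.

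**4. Sex: route through the plan's tests.** With estimated mean and SD (the Lilliefors form of Kolmogorov-Smirnov), splits of 3, 5, 7 or 10 of 15 are all rejected as non-normal (p about 0.001). The plan's rule therefore sends sex to Mann-Whitney.

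**5. Sex: effect of that route.** On a binary variable, the squared tie-corrected Mann-Whitney statistic without continuity correction equals chi-square × (N − 1)/N. For 12/15 against 6/15:

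- chi-square = 30 × (12 × 9 − 3 × 6)² / (15 × 15 × 18 × 12) = 30 × 8100/48600 = 5.00, p = 0.025
- Mann-Whitney z² = 5.00 × 29/30 = 4.83, p = 0.028

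All 16 × 16 possible sex tables were then enumerated with exact binomial weights, with the same true share of one sex in both groups, from 0.3 to 0.7:

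| Test | Type I error at nominal 0.05 | p, 12/15 v 6/15 | p, 10/15 v 7/15 |
|---|---|---|---|
| t on 0/1 codes | 0.046 to 0.055 | 0.025 | 0.28 |
| Mann-Whitney | 0.040 to 0.043 | 0.028 | 0.28 |
| Chi-square, uncorrected | 0.046 to 0.055 | 0.025 | 0.27 |
| Fisher's exact | 0.016 to 0.017 | 0.060 | 0.46 |

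The planned tests behave almost like chi-square. Fisher's test is clearly more conservative.

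**The case against.** The best defence is that the sentence is a slip. Mean and SD or median and IQR, followed at once by a normality check, is how one writes about continuous variables, and nobody is likely to report a mean walking aid. That may well be so. The plan would then have a sound rule for continuous variables and none for categorical ones, and the correction is the same.

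Several stronger readings are tempting, and the documents do not support them:

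- **Walking aid and assistance get the wrong test.** They are outcomes. The t and Mann-Whitney sentence in 7.2 covers demographic variables only, and 4.2.2 makes the walking items descriptive. Only the general synopsis sentence on differences in outcome measures could be stretched to reach them, and it does not name them.
- **The summary for sex is meaningless.** The mean of a 0/1 code is the proportion.
- **Very different aid distributions would look identical.** With codes 0, 1, 2, fifteen patients on crutches and a 7/1/7 split both have mean 1.0. But the plan also reports SD (0 against 1.0) or IQR (1 to 1 against 0 to 2), which separates them.
- **Walking autonomy is half of the functional-ability endpoint.** No such weight is given. The synopsis defines functional ability by the TUG alone, and maximum distance, one of the three walking items, is numeric if recorded as a length.

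It is also fair to say that nothing in the plan depends on the baseline sex comparison. Replacing the planned test by Fisher's alone would miss at 0.05 an imbalance such as 12/15 against 6/15 that the planned route would flag. That bears on how the fix is worded.

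**Conclusion.** The point stands as a minor correction to a rule in the analysis section. As written, 7.2 gives an unordered walking-aid variable a code-dependent summary and does not report how many patients need supervision or assistance. Sex is mis-specified as well, but by the enumeration above the choice between Mann-Whitney and chi-square makes little numerical difference.

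This rests on two assumptions. The first is that sex and age are the demographic variables. This is inferred from the data-protection text in 10.2; the data collection form (Attachment B) is not included in the text reviewed. The second is the set of illustrative splits, codes and true shares, since the documents supply none.

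The impact is confined to descriptive tables and the baseline sex comparison. A reader might infer that the trial's main results are at risk. They are not: the EMG analysis, the NRS and TUG regressions and the sample size are unaffected.

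**What to change.** Replace the descriptive sentence in 7.2, and limit the test rules, along these lines:

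*Continuous variables will be described by mean and SD or median and IQR; categorical variables (sex, walking aid, supervision or assistance) by counts and percentages. Sex will be compared between groups by chi-square or Fisher's exact test. Kolmogorov-Smirnov, t and Mann-Whitney apply to non-categorical variables only.*

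It would help to state in advance which of the two tests for sex is used and when, because Fisher's test is conservative with 15 per group (type I error about 0.016). Maximum distance, if recorded as a length, stays under the rule for continuous variables.

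The cost is one reworded sentence and its qualifiers in 7.2. Data collection and sample size do not change.

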4.1 General aims

The objective of the study is to evaluate possible differences in quadriceps muscular activation after TKA during the acute phase, with a comparison with healthy subjects. Moreover, it will be investigated whether any correlation exists between the outcomes obtained, the pain reported by the patient and his or her functional ability.

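### The single repeated-measures ANOVA in section 7.2 does not secure the post-operative comparison with healthy subjects, because controls have one session, patients have three, and no session or contrast is named

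*Combined protocol and SAP*

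**What the plan says.** Section 4.1 sets the objective: to "evaluate possible differences in quadriceps muscular activation after TKA during the acute phase, with a comparison with healthy subjects". Section 4.2.1 places the primary outcome in three muscles, "more specifically of the vastus medialis, lateralis and rectus femoris muscles, by means of electromyographic signal acquisition", and section 6.1 lists three tasks, each done twice.

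The measurement schedule in section 6.1 differs by group. For patients: "The assessment sessions will be conducted the day before the operation and on the first and third postoperative day". For controls: "The control group will be exposed once to the same assessments, with the EMG applied on the quadriceps muscle of the dominant limb". Section 7.1 plans 15 subjects per group.

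Section 7.2 then states: "The mixed models ANOVA test for repeated measures will be used to analyse possible differences inter-groups and intra-groups". It adds: "A post hoc analysis will be conducted in the eventuality of significant outcomes". In that section the t test and the Mann-Whitney test have another purpose; they "will be used to verify the pre-intervention homogeneity of the demographic variables". The synopsis is broader: it lists a t test or non-parametric equivalent for the outcome measures alongside the mixed ANOVA, but attaches no session to either.

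**The concern.** The objective needs patients after surgery set against healthy subjects. The named method is usually run with group as the between-subject factor and session as the within-subject factor, and that layout assumes every subject is seen at every session. Here no control is.

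An analyst following section 7.2 could lose the healthy comparison altogether. The analyst could also report a group effect whose meaning depends on how the controls' single visit was labelled in the data file. Section 7.2 places the analysis after data collection ends, so the choice would be made with the results in hand, against a 0.05 threshold. Task and muscle, which the primary endpoint depends on, have no stated place in the model either.

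**Working it through.** The plan gives no effect size, SD or power, so there is no figure of its own to reproduce. The check is structural.

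**Inputs.** 15 controls and 15 patients (7.1); 1 control session and 3 patient sessions (6.1); 3 muscles (4.2.1); 3 tasks (6.1).

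**Step 1: cells filled.**

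| Group | Day -1 | Day 1 | Day 3 |
|---|---|---|---|
| Patients | 15 | 15 | 15 |
| Controls | one session only, 15 subjects, no day assigned | | |

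- Cells in the full layout: 2 × 3 = 6. Observed: 3 + 1 = 4. Empty: 2.
- Crossed with task and muscle: 6 × 9 = 54 cells, of which 2 × 9 = 18 are empty.
- Subject-sessions: 15 × 3 + 15 × 1 = 60, against 30 × 3 = 90 in a full layout.

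**Step 2: group × session model.** Parameters: intercept, group, day 1, day 3, group × day 1, group × day 3, so 6. Four distinct cell means give a design matrix of rank 4, whichever day the controls are coded to. The interaction cannot be estimated. A repeated-measures ANOVA that requires all three sessions from each subject keeps 0 of 15 controls.

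**Step 3: group + session model.** Four parameters, rank 4, so it can be fitted and keeps all 30 subjects. Let H be the healthy mean, P the pre-operative patient–healthy difference, and D1 and D3 the changes in patients from day -1 to days 1 and 3. The patient means are H + P, H + P + D1 and H + P + D3. The model is a + g·(patient) + s1·(day 1) + s3·(day 3). Patients fix s1 = D1, s3 = D3 and a + g = H + P. The controls then fix a:

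| Controls coded as | a | Group term g | Example: P = -0.3, D1 = -1, D3 = -0.5 |
|---|---|---|---|
| Day -1 | H | P | -0.3 |
| Day 1 | H - D1 | P + D1 | -0.3 - 1 = -1.3 |
| Day 3 | H - D3 | P + D3 | -0.3 - 0.5 = -0.8 |

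The example values are assumptions for illustration; the algebra is not. The day terms stay at -1 and -0.5 throughout, so the within-patient changes are unaffected. Only the between-group term moves.

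**Step 4: group × task × muscle at one session.** Cells: 2 × 3 × 3 = 18, all filled. This is a sound analysis, but someone must choose day 1, day 3 or both.

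**Step 5: can the rest of the plan make that choice?**
- The synopsis t test on outcomes names no session, and section 7.2 confines its t tests to demographic variables.
- The post hoc sentence waits for a significant result and does not say which effect triggers it or which contrasts follow.
- With two post-operative sessions, three muscles and three tasks, 2 × 3 × 3 = 18 patient-versus-healthy contrasts fit the objective. None is singled out.

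**The case against.** The best defence is that section 7.2 never says session is the repeated factor. Tasks and muscles are recorded in every subject under the same set-up, so an ANOVA over task and muscle at one session has no empty cells. This stands. The rank deficiency and the loss of the controls are consequences of one reading, not of the text as such. That reading is still the natural one, because the sentence covers changes within groups and only patients have repeated sessions. The alternative reading also lacks a named session.

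Second, the day -1 coding is not a serious candidate for the main result. Section 4.1 asks about the period after surgery, and the synopsis gives baseline outcome measures a separate homogeneity check. This also stands. It narrows the open choice to day 1, day 3 or both, but does not settle it.

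Third, the study claims little: "it is estimated that this sample will be enough to obtain a preliminary valuation of the differences between groups". That tempers the severity. However, the difference between groups is the very quantity left undefined.

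Two stronger inferences should be resisted. A reader might conclude that the study cannot be analysed or that its data are compromised. Steps 3 and 4 show otherwise, since all four group-session means can be estimated. A reader might also want to attach a false-positive rate to the open choice. The documents give no variance components and do not define the gate before post hoc testing, so any such rate would rest on assumptions.

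**Conclusion.** The point holds as a mismatch between the stated method and the design, and it should be fixed. Without any assumption: 2 of 6 group-session cells are empty, and no session or contrast is named for the comparison in section 4.1. If session is the repeated factor, the interaction is not estimable, and complete-row analysis removes all 15 controls. If only main effects are fitted, the group term takes a different meaning for each coding of the control visit. Under any of these readings the post-operative comparison with healthy subjects is not secured.

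Two limits apply. The ANOVA sentence does not mention EMG; that it applies to EMG is inferred from section 7.1, which makes the EMG signal the primary outcome. The study scheme in Attachment A was not available for this check and may say more.

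**What to change.** In section 7.2, with the synopsis aligned, replace the single ANOVA with two stated parts:

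- **(a)** a patients-only repeated-measures analysis over day -1, day 1 and day 3;
- **(b)** patient-versus-healthy comparisons at day 1 and at day 3.

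Both parts take task and muscle as within-subject factors, and the text should say how the two repetitions of each task are combined.

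A mixed model with a four-level factor (healthy; patient day -1; day 1; day 3) and the same named contrasts would also serve. It should state its variance assumptions, because subject and session variance cannot be separated in controls seen once. With task and muscle fully crossed it has 4 × 3 × 3 = 36 cell means for 30 subjects, so the two-part analysis is simpler. Choose one in advance.

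Name one post-operative patient-versus-healthy contrast as primary, including its task and muscle. Label the others secondary or adjust them, for example by Holm. Say which session any t test on outcomes uses.

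**Cost.** Visits, sample and data are unchanged; the analysis is slightly longer. Adjustment costs some power. As an illustration, take a two-sided test, 15 per group, 80% power and the normal approximation, in SDs of the tested variable. The detectable difference is (1.960 + 0.842) × √(2/15) = 1.02 SD at 0.05. If the primary contrast is day 1 or day 3 versus healthy, three contrasts remain: the other of those two, and day 1 and day 3 versus day -1. At Holm's strictest step for three contrasts, 0.05/3, the between-group one needs (2.394 + 0.842) × √(2/15) = 1.18 SD. The primary contrast stays at 0.05 and loses nothing.
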